3.8.3 Dose constraints

A goal V110 (of escalated dose/PTV tumor) will be <5%. The urethral dose will be limited to 105% PTV tumor dose. Bladder wall will be limited to 105% of the prescribed dose. Rectal wall will be limited to 100% of the prescribed PTV tumor dose if the area is not included in the PTV tumor (Rectal wall for normal tissue dose limits will be defined as the rectal wall minus the PTV tumor volume).

3.8.4 Treatment Delivery

An SBRT set up will be used for all treatments. Treatment will be delivered in 5 fractions over a span of 7-14 days. Image guidance will include pre-treatment cone beam CT as per standard of care. An additional post-treatment cone beam CT after each fraction will be obtained to assess intrafraction motion. Calypso beacons will be utilized for real time tumor tracking as per the standard of care if implanted.

3.9 COST AND COMPENSATION

3.9.1 Costs

NIH does not bill health insurance companies or participants for any research or related clinical care that participants receive at the NIH Clinical Center. If some tests and procedures are performed outside the NIH Clinical Center, participants may have to pay for these costs if they are not covered by an insurance company. Medicines that are not part of the study treatment will not be provided or paid for by the NIH Clinical Center.

3.9.2 Compensation

Participants will not be compensated on this study.

3.9.3 Reimbursement

The NCI will cover the costs of some expenses associated with protocol participation. Some of these costs may be paid directly by the NIH and some may be reimbursed to the participant/guardian as appropriate. The amount and form of these payments are determined by the NCI Travel and Lodging Reimbursement Policy.

3.10 CRITERIA FOR REMOVAL FROM PROTOCOL THERAPY AND OFF STUDY CRITERIA

Prior to removal from study, effort must be made to have all subjects complete a safety visit approximately 90 days following the last dose of study therapy.

3.10.1 Criteria for removal from protocol therapy

- Completion of protocol therapy
- Progressive disease
- Participant requests to be withdrawn from active therapy
- Unacceptable Toxicity as defined in Section **3.1.1**
- Investigator discretion

3.10.2 Off-Study Criteria

- Completed study follow-up period
- Participant requests to be withdrawn from study
- Death
- Investigator discretion
- Non-compliance with follow-up visits or protocol mandated procedures

- Permanent loss of capacity to consent
- Lost to follow-up

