3.1.1 Dose Limiting Toxicity

Dose-limiting toxicities will be defined as follows (during treatment and within the first three weeks after treatment):

- Grade 3 rectal, small bowel, or urinary toxicity that does not resolve to Grade 2 or less within 4 days with appropriate medical management
- Other grade 3 in-field toxicities attributable to SBRT that do not resolve to Grade 2 or less within 4 days with appropriate medical management
- Delays of more than one week in completing radiation treatment due to toxicity (cumulative duration of delay over the course of the entire treatment).

Additionally, late toxicities (those that occur after 90 days following completion of treatment) will be followed and scored but will not be used for escalation with the following exception.

If Grade ≥ 4 late bowel or Grade ≥ 3 bladder injury is observed in 2 patients in any cohort, dose escalation will be terminated in that arm and the dose below that dose level in which the toxicity was observed will be considered the MTD. The criteria for late DLT for bladder were changed to Grade 3 to Grade 4 via amendment version date 04/13/2021, and should apply retroactively to all prior participants. MTD will be determined for each arm separately. Early and late toxicities used for assessment of DLTs should be attributable (possible, probable or definite) to SBRT. Changes in sexual and erectile function will not be considered a DLT.

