4. PSA failure after definitive radiation as defined by the Phoenix criteria (PSA elevation at least 2 ng/dL above post-radiotherapy nadir). Serial PSA and serial correlative studies will be collected for two years post-treatment.
5. Post-Imaging research and diagnostic biopsies of areas in the prostate identified as suspicious and systematic biopsy. If recent systematic biopsies were obtained (within 5 months) systematic biopsies may not be repeated. Fiducial markers to guide radiation treatment will be implanted simultaneously. If biopsy tissue was obtained within 5 months on another protocol and is available for transfer, biopsy will not be repeated unless clinically indicated. Fiducials will not be implanted again if previously placed and visible.
6. Six months following treatment, patients in both arms will undergo repeat 18F-DCFPyL imaging only if pretreatment imaging was informative.
7. If an 18F-DCFPyL study was performed within 4 months prior to enrollment on a different protocol, it will not be repeated at baseline. In patients treated with androgen deprivation therapy that was initiated within 4 months of a DCFPyL obtained on another protocol, this DCFPyL scan may be used as the baseline scan if the patient remains on ADT and the scan was obtained within 12 months of enrollment.
8. +/- 2 weeks at and after 6 month time point.
9. May be completed by remote visit with a member of the study team (e.g., if the patient is not able to return to the NIH CC). Remote visits will be conducted in compliance with NIH, FDA regulations and local policy. A patient may be referred to their local provider or asked to come to the NIH CC for an in-person assessment, if clinically indicated, and at the discretion of the PI. In the case of any visits with participants' local providers, records will be obtained.
10. Vital signs may be omitted during follow up visits if a patient is unable to return at the NIH clinical center and if the clinical evaluation does not indicate a need for collection.
11. As PSA is a standardized test and the results are comparable across laboratories, if the patient is not able to return to the NIH Clinical center, PSA may be obtained locally. If biochemical failure (PSA elevation at least 2 ng/dL above post-radiotherapy nadir) is identified, the second measurement will be obtained for confirmation per **6.3.2**, ideally at the NIH Clinical Center.

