3.10.3 Lost to Follow-up

A participant will be considered lost to follow-up if he or she fails to return for 3 scheduled visits and is unable to be contacted by the study site staff.

The following actions must be taken if a participant fails to return to the clinic for a required study visit:

- The site will attempt to contact the participant and reschedule the missed visit and counsel the participant on the importance of maintaining the assigned visit schedule and ascertain if the participant wishes to and/or should continue in the study.
- Before a participant is deemed lost to follow-up, the investigator or designee will make every effort to regain contact with the participant (where possible, 3 telephone calls and, if necessary, an IRB approved certified letter to the participant's last known mailing address or local equivalent methods). These contact attempts should be documented in the participant's medical record or study file.
- Should the participant continue to be unreachable, he or she will be considered to have withdrawn from the study with a primary reason of lost to follow-up.

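### Section 3.10.2 allows a reachable, consenting man to be taken off study for non-compliance, with no provision for PSA, late-toxicity or vital-status follow-up afterwards; this can bias bPFS and can only lower the late-event count

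*Combined protocol and SAP*

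**What the plan says.** Section 3.10.2 gives the off-study criteria. One is "Non-compliance with follow-up visits or protocol mandated procedures". The same list contains "Completed study follow-up period", consent withdrawal, death, investigator discretion, permanent loss of capacity to consent, and loss to follow-up.

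Loss to follow-up has its own definition in 3.10.3: the man "fails to return for 3 scheduled visits and is unable to be contacted by the study site staff". Both conditions must hold, and the site must first try to reach and reschedule him.

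Before removal, 3.10 says "effort must be made to have all subjects complete a safety visit approximately 90 days following the last dose of study therapy". Section 3.1.1 says that "late toxicities (those that occur after 90 days following completion of treatment) will be followed and scored", and then gives them a decision role: "If Grade ≥ 4 late bowel or Grade ≥ 3 bladder injury is observed in 2 patients in any cohort", escalation ends in that arm and the level below becomes the MTD.

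The study calendar (3.6) is flexible. Clinical evaluation "May be completed by remote visit with a member of the study team" (footnote 9), PSA may be drawn locally (footnote 11), and for men unable to return, imaging may be delayed and research samples omitted (footnote 12).

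Section 3.5 sets PSA follow-up at two years. Section 10.4.3 estimates bPFS by Kaplan-Meier and gives no censoring rule for men taken off study. Under 10.3, one post-treatment PSA makes a man evaluable for bPFS, so a man removed later would presumably enter as a censored case.

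**The concern.** Because loss to follow-up is a separate bullet that requires failed contact, the non-compliance bullet adds men who can still be reached. The procedures that count are not listed. On its face the wording covers questionnaires (baseline plus nine follow-up visits), research blood and urine, and the 6-month MRI and PET scan. None of these is needed to record PSA failure, death, or late bowel or bladder injury.

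Two results need observation well past 90 days: bPFS at 1 and 2 years, and the late-injury count in 3.1.1. Men who stop cooperating because of symptoms or a rising PSA are not a random sample. Censoring them at removal breaks the Kaplan-Meier assumption that censored men have the same future risk as those who remain. The late-injury rule counts patients without adjusting for time observed, so shorter follow-up can reduce the count but never raise it.

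**Working it through.** The plan states no figure on this point to reproduce. The check compares the text and then illustrates the size.

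**1. Does anything retain the man?**
- Non-compliance (3.10.2): no threshold and no requirement of failed contact.
- Loss to follow-up (3.10.3): three missed visits and failed contact. A reachable man who has missed one or two visits is not lost, yet can be removed under 3.10.2.
- Safety visit (3.10): at about 90 days, and an effort only. The late window in 3.1.1 opens after 90 days, so this visit precedes the period at risk.
- Footnotes 9 to 12: these ease attendance, mainly for men unable to return. None covers refusal of a whole procedure or overrides 3.10.2.
- After off-study: no section describes further collection. That collection ends is an inference, but the natural one, since completing follow-up is on the same list.

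**2. bPFS.** Inputs: true 2-year bPFS 75% (the brachytherapy reference rate in 10.1); removed fraction f = 4/46 = 8.7% (the accrual ceiling of 46 less 42 evaluable, 10.2), or 20% (assumed); removal uniform over months a to b (assumed); hazard ratio HR of removed men against the others, 2 to 4 (assumed); constant hazards.

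Solve (1 − f)·exp(−24h) + f·exp(−24·HR·h) = 0.75 for h. For f = 4/46 and HR = 2, h = 0.01113 per month: 0.913 × 0.7656 + 0.087 × 0.586 = 0.750.

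Let G(t) be the proportion of the removed group not yet removed: 1 before month a, (b − t)/(b − a) from a to b, then 0. The value that Kaplan-Meier approaches is

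exp{ −∫₀²⁴ [(1 − f)h·e^(−ht) + f·HR·h·e^(−HR·h·t)·G] / [(1 − f)e^(−ht) + f·e^(−HR·h·t)·G] dt }.

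| Removed | Months | HR 1 | HR 2 | HR 4 |
|---|---|---|---|---|
| 8.7% | 3–24 | 75.0% | 75.6% | 76.3% |
| 20% | 3–24 | 75.0% | 76.3% | 77.6% |
| 20% | 3–12 | 75.0% | 77.2% | 79.5% |

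The shift is 0.6 to 1.3 points in the first row and at most 79.5 − 75.0 = 4.5 points in the last. For scale, the simple binomial standard error at 75% is √(0.75 × 0.25/42) = 6.7 points for 42 men and √(0.75 × 0.25/21) = 9.4 points for 21.

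The direction is not fixed. Take 21 men with 5 true failures (1 − 5/21 = 76.2%) and remove 2 before any event. The estimate is 1 − 5/19 = 73.7% if neither would have failed, and 1 − 3/19 = 84.2% if both would have. These are extreme bounds.

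**3. Late-injury rule.** Inputs: 12 men at a level (6, plus the 6 expansion patients in Table 3); true late risk p = 15% (assumed) or 2/29 = 6.9% (Grade 3 or higher GU toxicity in the prior SBRT series, 1.2.1). P(2 or more) = 1 − (1 − p)¹² − 12p(1 − p)¹¹.
- p = 0.15: 1 − 0.142 − 0.301 = 0.557.
- 20% of men lose half their window, p = 0.15 × (1 − 0.2 × 0.5) = 0.135: 0.496.
- 30% do so, p = 0.15 × (1 − 0.3 × 0.5) = 0.1275: 0.464.
- Two of the 12 removed before any event (n = 10): 0.557 falls to 0.456 at 15%, and 0.199 falls to 0.148 at 6.9%.

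These falls occur even when removal is unrelated to toxicity. If exactly two men at a level would have qualifying events, one random early removal hides one of them with probability 1 − C(n−1, 2)/C(n, 2): 0.33 for n = 6 and 0.17 for n = 12.

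**The case against.** **Removal may be rare, and the bPFS effect small.** Section 10.2 expects minimal dropout. At its own allowance of 4 in 46 the shift is about 1 point, against a standard error of 6.7 points or more, for a descriptive secondary endpoint. The 20% and 30% fractions and the hazard ratios are assumptions. This stands, and it limits the claim to *can bias*. A reader might infer that the rule does bias bPFS; the documents do not show that removal would be related to outcome.

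**Refusal is partly handled.** Besides footnote 12, section 11.4.1.10 lets men skip questions that make them uncomfortable, and 3.10.3 tells the site to ask whether the man wishes to, and should, continue. So 3.10.2 and 3.10.3 are separate grounds, not a contradiction, and nothing says that one refused questionnaire must lead to removal. This stands too, but no written limit prevents it.

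**The MTD risk is mostly past.** Neither arm will go to level 3. Arm 1 is held at level 1, the lowest, so the rule has no lower level to name there. Going forward it can move the MTD only at Arm 2 level 2. This is correct.

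**A stronger reading of Arm 1.** A reader might infer from 1.2.5 that losing either of the two level 2 men with Grade 3 urinary events would have changed the primary result. The documents do not support that. Those events did not meet the criterion then in force. The late bladder criterion was amended afterwards, retroactively, so that level 1 could be considered the MTD. What the sponsor would have done after one event cannot be known.

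**Conclusion.** The gap is real: the off-study rule as written reaches consenting, contactable men, and nothing keeps them under observation for the results that need 24 months. The effect on bPFS depends on removal being related to outcome and on how many men are removed and when. It is nil at a hazard ratio of 1, small at the plan's own dropout allowance, and 4.5 points in the most adverse Kaplan-Meier scenario above. The effect on the late-injury count runs one way only. It bears on the MTD at Arm 2 level 2 and on the late-toxicity profile in both arms. This is a worthwhile, low-cost improvement, not a flaw that invalidates the design.

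**What to change.** - **3.10.2.** Replace the non-compliance bullet with a rule that a man who declines a visit, scan, questionnaire or sample is withdrawn from that procedure only. While he consents, he stays in follow-up to 24 months for PSA, late bowel and bladder toxicity and vital status, by remote contact or local records. State that investigator discretion is not to be used to end this follow-up for non-compliance. Leave the loss-of-capacity bullet for the sponsor to address separately.
- **3.6 footnote 11 and 6.3.3.** Reconcile them. The footnote allows local PSA because results are comparable across laboratories; 6.3.3 counts only Clinical Center values because ranges vary. Until this is settled, a retained man with only local PSA gives no usable bPFS value.
- **6.1 and 3.1.1.** Reconcile them. After the 90-day collection period, 6.1 requires recording only of serious, related events, while 3.1.1 relies on late bladder injury from Grade 3, which need not be serious.
- **10.4.3.** Report the number censored before 24 months, by reason.

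The cost is a short amendment to several sections and some staff time for remote contacts, which footnote 9 already permits.

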3.10.3 Lost to Follow-up

A participant will be considered lost to follow-up if he or she fails to return for 3 scheduled visits and is unable to be contacted by the study site staff.

The following actions must be taken if a participant fails to return to the clinic for a required study visit:

- The site will attempt to contact the participant and reschedule the missed visit and counsel the participant on the importance of maintaining the assigned visit schedule and ascertain if the participant wishes to and/or should continue in the study.
- Before a participant is deemed lost to follow-up, the investigator or designee will make every effort to regain contact with the participant (where possible, 3 telephone calls and, if necessary, an IRB approved certified letter to the participant's last known mailing address or local equivalent methods). These contact attempts should be documented in the participant's medical record or study file.
- Should the participant continue to be unreachable, he or she will be considered to have withdrawn from the study with a primary reason of lost to follow-up.

4 CONCOMITANT MEDICATIONS/MEASURES

Supportive care with blood components, antibiotics, analgesics, and general medical therapy will be provided if the need relates to the performance of protocol assessments (biopsy and imaging procedures) or to treat side effects of therapy. Every effort will be made to refer the patient to their collaborating physician in the community for care unrelated to the protocol therapy or procedures. There are no limitations on the type of non-investigational concurrent medications allowed, as in general, these patients do not receive additional therapy for prostate cancer after radiotherapy, with the exception of hormonal therapy, which will not be delivered on this trial. Concurrent use of androgen deprivation therapy will be allowed but discouraged.

Radiation related side effects will be managed as per the current standard of care without restrictions in medications or procedures that may be performed for management.

5 CORRELATIVE STUDIES FOR RESEARCH

5.1 BIOSPECIMEN COLLECTION

Tubes/media may be adjusted at the time of collection based upon materials available or to ensure the best samples are collected for planned analyses.

| Test/assay | Volume (approx.) | Type of tube | Collection point (+/- 48hrs) | Location of specimen analysis |
|-------------------|-------------------------|---------------------|--|--------------------------------------|
| Plasma | Up to 24 mL | EDTA | Baseline, 1 month post SBRT, q 3 months after SBRT | [name] [name] |
| | Up to 8 mL | Cell-Free DNA BCT | Baseline, q 3 months after SBRT | [name] |
| Urine | 15 mL | Sterile cup | Baseline, q 3 months after SBRT | [name] |
| Tumor biopsies | N/A | N/A | baseline | [name] lab |

5.1.1 Plasma

Plasma will be sampled at baseline and every three months after SBRT

Three 8 mL aliquots of blood will be obtained in EDTA containing tubes, and one 8 mL aliquot of blood will be obtained in a Cell-Free DNA blood collection tube (BCT), such as Streck BCT. Following collection, tubes will be immediately placed on ice and transferred to the laboratory of [name] for processing and storage, [name], [contact]. The Cell-Free DNA BCT aliquot will be transferred to the laboratory of [name], [name], [contact].

Plasma will be stored and batched for analysis.

Plasma assays in [name] laboratory will include ELISA/Bioplex analysis of predictive biomarkers recently identified by the [name] laboratory that correlate with tumor resistance to radiotherapy (70 analytes). Studies in [name] laboratory will include germline DNA studies (baseline only) and circulating tumor DNA levels. Plasma studies in [name] laboratory will include surface receptor analysis by nanoFACS and RNAseq, for exosome and extracellular RNA analysis.

5.1.2 Urine

Urine will be sampled at baseline and every three months after SBRT.

At least 15 mL of urine will be obtained in a sterile collection cup. Following collection, urine will be transferred to the laboratory of [name] for processing, measurement of creatinine concentration, and storage.

Urine will be stored and batched for analysis.

Urine assays will include ELISA analysis of predictive biomarkers recently identified by the [name] laboratory that correlate with tumor resistance to radiotherapy (70 analytes identified in tissue, screening for detection will occur in urine and plasma).

5.1.3 Prostate biopsy tissue

Prostate tissue will be sampled at baseline

Prostate biopsy tissue found to contain tumor will be stained for PSMA and somatostatin receptor. Additional neuroendocrine markers may also be stained (chromogranin A, NSE). If this work cannot be completed by the pathology collaborator, it will be referred for staining through a contract.

Prostate biopsy tissue will be collected into PaxGene preservative or snap frozen and subsequently transferred to the laboratory of [name]'s. Tumor tissue will be used for RNA analysis (RNAseq or microarray) and DNA analysis (targeted sequencing, exome sequencing, or whole genome sequencing). Research cores will be collected for additional analyses such as whole genome/exome sequencing and RNA seq. If adequate tumor tissue is not available for these analyses, targeted mutation testing may be performed.

5.2 SAMPLE STORAGE, TRACKING AND DISPOSITION

Samples will be ordered in CRIS and tracked through a Clinical Trial Data Management system. Should a CRIS screen not be available, the CRIS downtime procedures will be followed.

Samples will not be sent outside NIH without appropriate approvals and/or agreements, if required.

All samples will be labelled and catalogued with Lab Matrix in the laboratory of [name]. Samples transferred to [name] will be similarly catalogued in Lab Matrix. Samples will be stored at -80° C until use.

All specimens obtained in the protocol are used as defined in the protocol. Any specimens that are remaining at the completion of the protocol will be stored in the conditions described above. The study will remain open so long as sample or data analysis continues. Samples from consenting subjects will be stored until they are no longer of scientific value or if a subject withdraws consent for their continued use, at which time they will be destroyed. The PI will record any loss or unanticipated destruction of samples as a deviation. Reporting will be per the requirements of section [7.2](#).

Blood and urine samples may be subjected to protein or RNA analysis in the future to describe novel prognostic or predictive biomarkers.

If the patient withdraws consent the participant's data will be excluded from future distributions, but data that have already been distributed for approved research use will not be able to be retrieved.

5.3 SAMPLES FOR GENETIC/GENOMIC ANALYSIS

5.3.1 Description of the scope of genetic/genomic analysis

The anticipated analysis on whole blood DNA and tumor DNA will include whole exome or genome sequencing and targeted analysis in blood as described in Section [5.1](#).

5.3.2 Description of how privacy and confidentiality of medical information/biological specimens will be maximized

Samples will be bar coded for storage and personal identifiers will be removed. Names and demographic data will be linked to bar codes in the password protected LabMatrix database. This data will be accessible only by the PI and the research nurses within the ROB.

Samples provided to CCR collaborators will be barcoded. No personally identifiable information will be released to [name].

Data from genomic and genetic data will be deposited in dbGAP and released in accordance with NIH guidelines.

As part of study efforts to provide confidentiality of subject information, this study will obtain a Certificate of Confidentiality. Please refer to Section [12.4](#).

